9.4 Demographics and Baseline Characteristics

Demographic data to be collected will include age, gender, and number of years from onset of memory complaints in addition to CDR level (as derived from QDRS score) gathered at baseline and final follow-up (three months post-baseline). Results may be stratified by CDR at baseline to see if there is a correlation between baseline CDR and strength of clinical response.

9.5 Statistical Analysis of Endpoints

Based on published annual progression rates ranging from 15-35%, the investigative team determined that this study subset could yield a proportional expected progression rate of 4-9% among study participants over the 3-month study duration. (Maioli et al., 2007; McKann et al., 2011; Amieva et al., 2009; Mitchell & Shiri-Feshki, 2009; Schmidtke & Hermeneit, 2008; Albert et al., 2011; Mashour et al., 2019). Statistical analysis for primary and secondary endpoints will utilize standard evaluations for categorical data.

Primary endpoints will involve a comparison of neurophysiological health as evaluated by multi-modal brain MRIs obtained at baseline and post-intervention termination (3 months). Specifically, multi-modal MRI endpoints will include: An increase or stabilization in glutathione levels (as measured by magnetic resonance spectroscopy, MRS) compared to baseline. Patients with cognitive decline often show characteristic change in MRS or volumetric evaluation compared to age-matched controls (Kuhn et al. 2021); Stabilized and/or improved dendritic density compared to baseline (as measured by diffusion tensor imaging, DTI-NODDI); Enhancement of arterial signal compared to baseline (as quantified by arterial spin labeling, ASL). Patients with cognitive decline often have decreased perfusion in temporal parietal or frontal regions of the brain with ASL perfusion (Kuhn et al. 2021); Increased functional connectivity of the nucleus basalis of Meynert (NBM) with both hippocampi as well as between both hippocampi compared to baseline, as visualized by seed analysis of blood-oxygen level dependent (BOLD) imaging as well as increased neurovascular coupling compared to baseline.

9.5.1 Statistical Analysis for Primary Imaging Endpoints

Repeated Measures ANOVAs (RMANOVAs) will be employed to evaluate whether the participants who successfully complete the treatment protocol demonstrate differential improvement in cognition over time with global and domain level mean T-scores as the outcome variable of interest. The same ANOVA-based statistical analysis paradigms will be applied to the neuroimaging data after it is preprocessed. RMANOVAs will be run to determine whether the treatment group demonstrated improvements in the below imaging modalities, from baseline to study completion. Age, sex, and education, as statistically indicated, will be included as additional regressors. Correlation analyses will then be conducted to determine whether absolute change in domain level as measured by neuropsychological evaluation and global cognitive performance is associated with absolute change in the following imaging parameters. To compare individuals from the study population with a “normal” population, Z-score will be calculated for each individual for each component of the toolbox as well as compute a global-cognitive Z-score metric. This will allow the comparison of individual participants to a large population of normal derived from the published literature (e.g. Human Connectome Project).

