2.2 Secondary Objective(s)

Secondary endpoints will include a longitudinal comparison of metabolic and serological analysis (specifically measures of glucose and insulin homeostasis); the level of cognitive impairment as defined by neuropsychological testing. Neuropsychological testing measures will include the Quick Dementia Rating Scale (QDRS), Clinical Dementia Rating (CDR) score as estimated by the QDRS, the Alzheimer's Disease Assessment Scale (ADAS-Cog12), the Mini-Mental State Examination (MMSE), and the Montreal Cognitive Assessment (MoCA).

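### Section 9.5.1 analyses cognitive T-scores, domain scores and toolbox Z-scores that the trial's battery, as scored in the plan, does not produce

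*Combined protocol and SAP*

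**What the plan says.** Section 9.5.1 describes three separate cognitive analyses, each with its own variable.

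- The cognitive repeated-measures ANOVA takes "global and domain level mean T-scores as the outcome variable of interest".
- The imaging-cognition correlations ask whether "absolute change in domain level as measured by neuropsychological evaluation and global cognitive performance is associated with absolute change in the following imaging parameters".
- For a comparison with a normal population, a "Z-score will be calculated for each individual for each component of the toolbox as well as compute a global-cognitive Z-score metric". The norms are to come from published literature, with the Human Connectome Project given only as an example.

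Section 2.2 sets out what is measured: "Neuropsychological testing measures will include the Quick Dementia Rating Scale (QDRS), Clinical Dementia Rating (CDR) score as estimated by the QDRS", followed by ADAS-Cog12, MMSE and MoCA. Sections 6, 7.1 and 7.5 repeat this list at baseline and three months. Section 6 adds a Global Rating of Change at completion only.

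Section 9.5.2 gives the scoring. ADAS-Cog is an error total from 0 to 70, MMSE and MoCA are totals from 0 to 30, and the QDRS has ten items whose total is converted to a CDR level.

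**The concern.** The variables in Section 9.5.1 and the data in Sections 2.2, 6, 7 and 9.5.2 do not meet. Nothing collected is described as a T-score, a domain score or a component of a toolbox, so an analyst who follows Section 9.5.1 must first decide what the cognitive variable is. This is a different matter from which test to apply. The plan also assigns MMRM (Section 9.1) and paired t-tests (Section 9.5.2) to the cognitive measures, but settling on one method would still leave Section 9.5.1 without a defined outcome.

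The stake is the freedom this leaves. There is no control group (Section 5.1.2) and no blinding (Section 5.5), so the choice of score, or the construction of a composite, could be made with results in view. A reported association between MRI change and cognitive change could then not be distinguished from the best of several attempts.

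**Working it through.** **Step 1. The plan's own figure.** Section 9.2 gives 20 completers, 20% attrition and 25 enrolled. 20 / (1 − 0.20) = 25, which reproduces. The point does not depend on this figure, which only fixes the scale of the study.

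**Step 2. Variables named against variables available.**

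| Analysis in 9.5.1 | Variable named | What the battery offers | What is missing |
|---|---|---|---|
| Cognitive ANOVA | Global and domain mean T-scores | Totals for QDRS, MMSE, MoCA, ADAS-Cog; CDR level | T-score conversion, norms, domain mapping, rule for the mean |
| Correlation with imaging change | Domain-level and global cognitive change | Change in those totals | Domain scores, a global score, or a named scale |
| Comparison with normals | Z per toolbox component, plus a global Z | Same totals | The toolbox, its components, norms for these scales, composite rule |

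Section 9.5.2 does mention content areas: the parts of the ADAS-Cog, the abilities covered by MMSE and MoCA, and the five cognitive and five functional QDRS items. These are descriptions of content. No score is defined from any of them.

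**Step 3. Is the definition deferred elsewhere?** Section 9.1 defers to the SAP only the supportive analyses for missing data. No section defers the cognitive scores.

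**Step 4. How many separate scales could be chosen?** Five measures are listed, but the CDR level is computed from the QDRS, so four are measured separately: QDRS, MMSE, MoCA and ADAS-Cog. The Global Rating of Change has no baseline value and yields no change from baseline.

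**Step 5. Size of the freedom.** Take one imaging measure, no true association, and a test at 0.05 (Section 9.1) for each of k scales, reporting whichever is significant. With independent tests, the chance of at least one false association is 1 − 0.95^k.

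- k = 4: 0.95^4 = 0.8145, so 1 − 0.8145 = 18.5%.
- Relative to the nominal level: 0.185 / 0.05 = 3.7 times.

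The four scales rate the same patients' cognitive state, so their changes are likely to be positively correlated and the true figure lower. The documents give no correlations among them, so 18.5% is a ceiling for choice among these four totals. It does not count composites built from items, and it is per imaging measure.

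**Step 6. An ambiguity in the correlation.** Absolute change can mean change in raw units or change without sign. The second reading would treat improvement and decline alike. Naming signed change removes the doubt.

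**The case against.** The strongest reply is that this is a gap in specification and not an impossibility. T- and Z-scores are rescalings of collected scores against norms, Section 9.5.1 says where norms would come from, and items of the listed scales could be grouped into domains. That stands: a reader might infer that the analyses can never be run, and the documents do not support this. What they lack is the norms, the mapping and the composite rule, without which the named variables do not exist.

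Three further inferences go too far.

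- A reader might infer that the MRI correlations are built on T-scores and the toolbox Z-score. They are not. The correlation sentence names domain-level and global change, the T-scores belong to the ANOVA, and the toolbox Z-score serves only the comparison with normals. Each is undefined, but for its own reason.
- A reader might infer that the primary MRI endpoints lose their main interpretive support. No section gives the correlation that role. Sections 2.1 and 9.5 define the primary endpoints as changes from baseline on MRI, which need no cognitive score. The secondary cognitive analyses in Sections 9.1 and 9.5.2 use the named scales.
- A reader might count five measures and obtain 1 − 0.95^5 = 22.6%. That treats the CDR level as independent of the QDRS from which it is computed.

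It can also be said that Section 9.5.1 promises multiplicity correction for all imaging analyses, across voxels and between analyses. Whether that reaches these correlations is arguable. Even if it does, a correction can count only the tests that are declared, not an undeclared choice of cognitive score.

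**Conclusion.** The point holds as a conflict between Section 9.5.1 and the battery: the cognitive ANOVA, the imaging-cognition correlations and the normative comparison each name variables that the listed scales, as scored in Section 9.5.2, do not produce. The text is wrong as written and should be changed, but the reach is limited to these three analyses.

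The size is at most an 18.5% chance of a false association per imaging measure, against a nominal 5%. This assumes one test at 0.05 for each of four separately measured scales, independence, no true association, and free selection among them. Positive correlation lowers it. The figure describes what the text permits and is not a claim that such selection would take place.

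**What to change.** Amend Section 9.5.1 before analysis:

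1. Replace the T-score outcome of the cognitive ANOVA with the total scores of the listed scales.
2. Name one collected total, as signed change from baseline, as the cognitive variable for the MRI correlations. The documents do not favour any one scale, so the choice is the sponsor's, provided it is fixed in advance.
3. If ADAS-Cog is named, first reconcile ADAS-Cog12 (Sections 2.2, 6, 7.1 and 7.5) with the 11-part, 0 to 70 description in Section 9.5.2. Otherwise one undefined variable replaces another.
4. Delete the toolbox and global-cognitive Z-score text, or restrict it to listed scales with named published norms.

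The cost is wording, plus the loss of domain-level analyses that are not defined at present. No new data, visits or participants are needed.

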9 PLANNED STATISTICAL METHODS

9.1 General Considerations

Statistical analyses will be performed by the statistician on staff with The Regenesis Project. Software for statistical analyses will include Microsoft Excel (version 14 or newer) and IBM SPSS Statistics for Windows, version 26 (IBM Corp., Armonk, N.Y., USA). Statistical analyses will be run to compare change from baseline at the post-intervention termination follow-up (three months after baseline) using a level of significance of 0.05.

A single unblinded interim analysis may be performed when 30% to 50% of the participants have completed the final follow-up timepoint. The purposes of this interim analysis are to declare futility, study discontinuation for overwhelming efficacy, or sample size re-estimation. The sample size will not be reduced based on interim data.

The primary analysis model for the efficacy endpoints will be an MMRM analysis. All available data will be included in these models with no imputation for missing data. Supportive analyses of efficacy data may be conducted to evaluate different methods of handling missing data (i.e., Last Observation Carried Forward, Baseline Observation Carried Forward, multiple imputation for missing data, etc.). These supportive analyses will be detailed in the SAP. Each endpoint within the neuropsychological testing family will be analyzed using MMRM analysis methods in a similar manner as to how the primary endpoints will be analyzed. Formal significance for a given hypothesis will only be declared if that hypothesis is significant and all hypotheses within the family preceding it are significant. This approach will ensure strong type 1 error control is present for all statistical tests conducted.

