9.2 Determination of Sample Size

Approximately 25 participants are expected to be enrolled in this Phase II trial to evaluate longitudinal findings from multimodal MRI among the population that is being studied. The study population is sufficiently broad and the conditions of interest are sufficiently prevalent so that recruitment of participants is not a limiting factor for the trial site.

The sample size was chosen according to a power analysis calculated with 80% power and a significance level of 0.05. To achieve completion data for at least 20 participants, enrollment of 25 participants will allow for 20% attrition while maintaining statistical integrity.

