Arterial Spin Labeling (ASL) data will be processed and analyzed using FSLs Bayesian Inference for ASL MRI (BASIL; Chappell, Groves, Whitcher & Woolrich, 2009; Woolrich, Chiarelli, Gallichan, Perthen & Lie, 2006). ASL scans yield a perfusion image with voxel values representing local perfusion rates; perfusion difference will be calculated (subtracting tagged/control pairs) and averaged to create a mean perfusion-weighted image (Chen, Wolk & Reddin, 2011). Quantification to cerebral blood flow (CBF) values (milliliters of blood per 100 g of tissue per minute) will be implemented using an estimate of the equilibrium magnetization of arterial blood and the mean perfusion values (Ahlgren, Wirestam, Knutsson & Petersen, 2018; Hernandez-Garcia & Jahanian, 2010). Given the variability of ASL across patients, CBF data will be examined as a ratio to mean grey matter signal.

Each participant's ASL data will be linearly registered to each his or her T1-weighted image; images will then be transferred to MNI space using non-linear registration in FSL. Within FSL, a voxel-wise between groups (normal vs MRI) comparison of perfusion, corrected for multiple comparisons, will be performed. A repeated measures comparison within subject for pre-vs post intervention ASL as well as between groups will be used to compare effects of NE3107 to normals. Demographic covariates will be included in the model as indicated. All imaging analyses will be corrected for multiple comparisons, both across voxel and between analyses.

Existing literature consistently demonstrates a dropout of signal seen in the temporal parietal lobes among individuals with dementia of the probable Alzheimer's type (Zhang, Gordon & Goldberg, 2017). The mean perfusion values per voxel in the temporal parietal regions will be measured and used to generate a statistical output of participant values relative to a normative, age-matched database. This will test the hypothesis that there will be either stabilization or improvement of voxel signal among participant scans compared with the normative database associated with NE3107.

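### The one-group pre/post RMANOVA chooses age, sex and education from the data without fixing their coding or the tested term; retained covariates entered raw and crossed with time would invalidate the test of change

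*Combined protocol and SAP*

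**What the plan says.** Section 9.5.1 sets the within-group test: "RMANOVAs will be run to determine whether the treatment group demonstrated improvements in the below imaging modalities, from baseline to study completion". It then adds: "Age, sex, and education, as statistically indicated, will be included as additional regressors". The same section's DTI/NODDI text repeats that RMANOVA compares values before and after treatment. For ASL it says "Demographic covariates will be included in the model as indicated", and the BOLD text lets the same covariates, plus neuropsychological assessment, enter as needed.

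Section 9.1 names Microsoft Excel and "IBM SPSS Statistics for Windows, version 26" as software, and tests change "using a level of significance of 0.05" without saying whether the test is one- or two-sided. Sections 9.1 and 9.3 also name MMRM as the primary efficacy model and list no covariates for it.

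Section 9.4 states: "Demographic data to be collected will include age, gender, and number of years from onset of memory complaints", together with CDR level. Education is not in that list.

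The plan does not state a criterion for when a covariate is indicated, a fixed covariate set, whether covariates are centred, or which term or contrast is the test of change.

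**The concern.** With one group and two time points, the RMANOVA time test is a test of mean change. Age, sex and education take the same value at both visits, so they cannot bias that mean. Adding them with a covariate-by-time term amounts to regressing the change score on them, and the time effect is then the intercept. If age is entered in years, the intercept is predicted change at age 0, although entry is limited to ages 50 to 89. The same holds for education at zero years.

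The stated rule brings a covariate in when the data point to it. That is when the slope on the covariate looks large, and so when the intercept at age 0 lies furthest from the mean change. What is at stake is the error rate of the RMANOVA-tested imaging endpoints, which Section 2.1 makes primary.

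**Working it through.** **The plan's own figures.** Section 9.2 says "To achieve completion data for at least 20 participants, enrollment of 25 participants will allow for 20% attrition". The inflation reproduces: 20/(1 − 0.20) = 25. It also says "The sample size was chosen according to a power analysis calculated with 80% power and a significance level of 0.05", but gives no effect size or SD of change, so 80% power with 20 completers cannot be reproduced. Solving backwards for a two-sided paired t-test with n = 20 gives a standardised change d = 0.66 (noncentrality 0.66 × √20 = 2.95).

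**Inputs from the documents.** 20 completers, alpha 0.05, ages 50 to 89, a target sex ratio of 50:50, and two time points.

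**Assumed inputs.** Two-sided testing. Age normal with mean 70 and SD 8, with SD 6 and uniform 50 to 89 as alternatives. Education mean 16 years, SD 2.5. Raw covariates crossed with time. A covariate is kept at p<0.05, because the plan gives no threshold.

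**Step 1: the tested term.** Model change as a + b × age. With raw age, a is change at age 0. Its standard error, relative to that of the mean change, is multiplied by about √(1 + (mean/SD)²):
- SD 8: √(1 + (70/8)²) = √77.56 = 8.8
- SD 6: √(1 + (70/6)²) = √137.1 = 11.7
- Uniform 50 to 89 (mean 69.5, SD 39/√12 = 11.26): √(1 + (69.5/11.26)²) = 6.3

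**Step 2: why selection raises the error.** The correlation between the estimates of a and b is −(mean/SD)/√(1 + (mean/SD)²) = −8.75/8.81 = −0.99. When mean change is zero, the test of a is therefore almost the test of b with its sign reversed. A covariate kept because b is significant will nearly always make a significant too.

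A rough ceiling follows. The chance that age or education is kept by luck is 1 − 0.95² = 9.75%. If every such retention produced a rejection, the error would be about 0.9025 × 5% + 9.75% = 14.3%. A balanced sex factor does no harm.

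**Step 3: simulation** (8,000 replicates per scenario, true mean change zero, ranges over the three age distributions):

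| Analysis | Age unrelated to change | r = 0.3 | r = 0.5 |
|---|---|---|---|
| Unadjusted change | about 5% | about 5% | about 5% |
| Raw, kept if p<0.05 | 12.2% to 13.7% | 29% to 30% | about 64% |
| Centred, kept if p<0.05 | 5.2% to 5.9% | 5.7% to 6.3% | 8.3% to 8.6% |
| Centred age, always in | about 5% | 5.5% to 6.0% | 8.1% to 8.4% |

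In the correlated columns the false rejections under raw entry fall almost all in one direction, opposite in sign to the age slope. The exact rates depend on how the screen is done, which the plan leaves open. Screening covariates jointly lowers the raw-entry rates in the correlated columns somewhat but leaves them far above 5%.

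The last two rows show that the small excess under centring at r = 0.5 does not come from selection. The adjusted test treats the sample's mean age as fixed. This is a reason to prefer the unadjusted test as the main one.

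**Step 4: power.** At d = 0.66, with age unrelated to change and raw covariates kept at p<0.05, the rejection rate stays at 79% to 80%. With r = 0.3 it is 73% to 78%. Part of this is rejection in the wrong direction, so it should not be read as preserved power.

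**The case against.** The documents do not say that covariates enter raw or crossed with time. They name the software and are silent on both points. If age enters only as a main effect, as it could in an MMRM with time plus age, it leaves the time estimate and its standard error unchanged. With centring, choosing covariates from the data costs under one point of type I error when age is unrelated to change. This stands, and it makes the size of the problem conditional. It does not remove the gap: the selection rule is written into the plan, and nothing in the plan rules out the harmful coding.

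Covariates are also not pointless. Centred ones that predict change reduce residual variance; at r = 0.3, power rises from 80% to about 82% or 83%. In the comparisons with normals or controls in the ASL and BOLD text, age can confound, and adjustment may be needed. Both points stand.

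Glutathione and NAA:Cr are tested by Wilcoxon signed-rank tests without covariates, so they fall outside the problem. Section 9.5.2 assigns paired t-tests to the secondary cognitive measures. The RMANOVA for cognition in Section 9.5.1 conflicts with that, but this is a separate matter.

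On education, the list in Section 9.4 need not be exhaustive. Sections 6.3 and 6.10 refer to fuller demographic forms. The omission is a loose end rather than proof that education is not collected.

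**Conclusion.** The concern holds in a limited form. For the within-group RMANOVA in the opening of Section 9.5.1 and in its DTI/NODDI text, the plan selects covariates from the data and fixes neither their coding nor the tested term. If retained covariates are entered raw and crossed with time, type I error is about 12% to 14% with age unrelated to change. It is about 30% to 65% if change correlates with age at 0.3 to 0.5 while mean change is zero. With centring it is about 5.5%, or roughly 6% to 9% with correlation. These figures rest on n = 20, the assumed age and education distributions, a p<0.05 screen and the assumed software behaviour.

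A reader might infer two stronger results that the documents do not support. One is that power collapses to about 6%. That needs raw age in every model, whereas the plan enters it only when indicated. The other is an error rate near 20%. That needs the analyst to pick the smallest p-value among all covariate sets, which no section describes.

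**What to change.** In Section 9.5.1, for the within-group pre/post test, delete the data-driven covariate rule and make unadjusted mean change from baseline the main analysis. If an adjusted version is wanted, fix the covariate set in advance, mean-centre the covariates, and name time at mean covariate values as the tested contrast. Report covariate-by-time effects as exploratory. Apply the same wording to the RMANOVA in the DTI/NODDI text. For the comparisons with normals or controls in the ASL and BOLD text, covariates may stay. If education remains a regressor, add it to the data listed in Section 9.4.

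The cost is a few sentences, and at most one data field if education is not already recorded. The small power gain from covariates that predict change is given up unless the centred set is pre-specified. No participants or procedures are affected.
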